## **3.0 PATIENT SELECTION**

### **3.1 Eligibility Criteria**

- 3.1.1 Patients' recurrences must have histologically confirmed ductal carcinoma in-situ, invasive ductal, medullary, papillary, colloid (mucinous), or tubular histologies.
- 3.1.2 Lesion size  $\leq 3$  cm treated with a tylectomy. Patients with clinically and radiographically negative axillas should not undergo an axillary lymph node dissection unless they did not have prior axillary lymph node sampling (i.e. previous cancer was DCIS).
- 3.1.3 Unifocal breast cancer recurrence.
- 3.1.4 Negative resection margins with at least a 2 mm margin from invasive and in-situ cancer or a negative re-excision.
- 3.1.5 Hormonal therapy is allowed. If chemotherapy is planned, the radiation is delivered first and chemotherapy must begin no earlier than two weeks following completion of radiation.
- 3.1.6 Patients must be  $\geq 18$  years of age.
- 3.1.7 Signed study-specific informed consent prior to study entry.

### **3.2 Ineligibility Criteria**

- 3.2.1 Patients with distant metastatic disease
- 3.2.2 Patients with invasive lobular carcinoma, extensive lobular carcinoma in-situ, extensive ductal carcinoma in-situ (spanning more than 3 cm), or nonepithelial breast malignancies such as lymphoma or sarcoma.
- 3.2.3 Patients with multicentric carcinoma (tumors in different quadrants of the breast or tumors separated by at least 4 cm). Palpable or radiographically suspicious contralateral

- axillary, ipsilateral or contralateral supraclavicular, infraclavicular, or internal mammary lymph nodes unless these are histologically or cytologically confirmed negative.
- 3.2.4 Extensive intraductal component (EIC) by the Harvard definition, i.e. 1) more than 25% of the invasive tumor is DCIS and DCIS present in adjacent breast tissue. Presence of an EIC increases the chance of local recurrence, and as such, one might not be a candidate for repeat breast conservation.
  - 3.2.5 Patients with Paget's disease of the nipple.
  - 3.2.6 Patients with skin involvement.
  - 3.2.7 Patients with collagen vascular disorders, specifically systemic lupus erythematosus, scleroderma, or dermatomyositis.
  - 3.2.8 Patients with psychiatric, neurologic, or addictive disorders that would preclude obtaining informed consent.
  - 3.2.9 Other malignancy, except non-melanomatous skin cancer, < 5 years prior to participation in this study.
  - 3.2.10 Patients who are pregnant or lactating due to potential fetal exposure to radiation and unknown effects of radiation on lactating females.
  - 3.2.11 Patients with known BRCA 1/BRCA 2 mutations.

#### **4.0 REGISTRATION PROCEDURES**

Investigators will register patients by contacting the Cancer Center Clinical Trials Unit study coordinator. Patients will be registered by the study coordinator online via the Clinical Trials Unit Oncore database. A registration card, copy of the informed consent, and copy of the signed eligibility checklist must be completed prior to a patient starting treatment.

#### **5.0 TREATMENT PLAN**

Patients enrolled on the study will receive partial breast irradiation delivered as 1) a single intra-operative dose of 21 Gy or 2) MammoSite® brachytherapy consisting of a dose of 34 Gy in 10 fractions delivered over 5 days. Patients will be followed for a period of five years following completion of radiation.

##### **5.1 Surgery**

- 5.1.1 Patients will undergo excisional biopsy or needle localization removal of the tumor.
- 5.1.2 Patients with margins < 2 mm undergo re-excision of the biopsy cavity.
- 5.1.3 For patients undergoing IORT, the skin around the excision site will be dissected and small skin flaps will be raised. The breast tissue is then loosely sutured so that the lateral margins are brought into apposition. The applicator will then be positioned to encompass the entire tumor bed with a 1 cm margin. After radiation has been delivered, sutures will be removed and the tumor bed will be closed in the typical fashion.

5.2 **Radiation Therapy** – Consultation via presentation at our multi-disciplinary breast conference between the surgeon, radiation oncologist and medical oncologist will take place to determine suitability for undergoing partial breast radiation and a recommendation will be made as to which modality is best suited for the patient. Clinical characteristics, including but not

limited to, distance of tumor from skin, patient's ability to tolerate another surgical procedure, patient's ability to come into the radiation department twice daily for treatment, will be considered in making this decision. All patients will be seen in consultation by the radiation oncologist prior to enrollment.

5.2.1 Intraoperative Radiation:

5.2.1a Applicator selection should allow for treatment of the tumor bed with a 1 cm radial margin.

5.2.1b Dosimetry on all applicators should be available to the radiation oncologist upon request in the operating room.

5.2.1c Energy of electrons should be such that the tumor cavity with a 1 cm margin will be covered by the 90% line. *The energy of the electrons will be at the discretion of the radiation oncologist and determined at the time of treatment to ensure proper coverage of the tumor cavity.*

5.2.1d A dose of 21 Gy will be prescribed to the 90% isodose line.

5.3.1 MammoSite® Brachytherapy:

5.3.1a Applicator Placement:

5.3.1a1 The MammoSite® applicator may be placed either at the time of surgery or in a separate procedure using ultrasound guidance after surgery. The MammoSite® applicator should be selected to best fit the cavity created by the surgical removal of the tumor.

5.3.1a2 The balloon of the MammoSite® applicator should be inflated with a saline/contrast mixture (maximum of 25% contrast) to fill the cavity at the time of placement. The balloon will remain inflated throughout the duration of the radiation and will be removed after the last fraction.

5.3.1a3 Post implant imaging should be performed after insertion of the MammoSite® to evaluate the patient for skin spacing, symmetry and conformance of the applicator.

5.3.1b Treatment Planning

5.3.1b1 CT image is recommended for treatment planning. Standard brachytherapy treatment planning will be conducted using commercially available software and equipment. The treatment should be performed using available high dose rate (HDR) brachytherapy.

5.3.1b2 CT imaging or plain orthogonal x-rays will be performed prior to treatment to ensure adequacy of implant.

5.3.1c Brachytherapy Treatment:

5.3.1c1 Brachytherapy should start between 3 - 7 days after implant.

5.3.1c2 The dose is 34 Gy prescribed to a depth of 1 cm from the balloon surface delivered over 10 fractions of 3.4 Gy over 5-10 days. The fractions are delivered twice a day with at least six hours separating each fraction.

5.3.1c3 All treatments should be done using a commercially available HDR and Ir radioactive sources.

5.3.1d Applicator Removal:

5.3.1d1 The removal of the applicator should be scheduled after the completion of brachytherapy.

5.3.1d2 The applicator should be removed using standard sterile technique.

5.3.1d3 The applicator exit/entrance site should be dressed according to standard medical practice.

#### 5.4 Data Safety and Monitoring Plan

This protocol will adhere to the policies of the Case Comprehensive Cancer Center Data and Safety Monitoring Plan, version 2 guidelines in accordance with NCI regulations. The Data and Safety Toxicity Committee will review all serious adverse events and toxicity reports as well as annual reviews.

### **6.0 MEASUREMENT OF EFFECT**

The endpoints of this study are as follows:

- 6.1 Determination ipsilateral breast tumor recurrence rates as well as tumor bed recurrence rates. The breast quadrant of recurrence will be recorded. Patients will be followed for a period of five years following completion of radiation.
- 6.2 Cosmetic outcome as determined by an established scale employed by the radiation oncologist and the surgeon.
- 6.3 Patient satisfaction with the procedure as determined by a questionnaire to be completed by the patients.
- 6.4 Wound healing and overall complication rate after partial breast re-irradiation.
- 6.5 Determination of which patients are best suited for each individual technique of performing partial breast irradiation. Measurement of this will be observational.

## 7.0 STUDY PARAMETERS

Study Parameters	Pre-Treatment	Follow-up
H&P/clinical evaluation	X	1 month after RT & Q3mos for one year, then annually for 5 years.
Mammogram	X	Ipsilateral breast 6 mos after dx, bilateral annually
CXR	X	Annually x 5 years
CT chest/abdomen/pelvis	X	If clinically indicated
Bone Scan	X	If clinically indicated
Cosmetic Evaluation/QOL assessment	X	1 month after RT & Q3mos for one year, and at 5 years.
Skin Assessment		Last day of RT
Breast MRI		If clinically indicated

## 8.0 STATISTICAL CONSIDERATIONS

The primary objective is to determine the feasibility of partial breast irradiation after repeat breast-conserving surgery for an IBTR. Thirty patients will be enrolled for this study and we expect to finish the enrollment within 5 years. For the safety of patients, interim analyses will be performed after 6, 12, 18 and 24 patients have reached 3 months and 1 year post treatment period. The protocol will remain open to enrollment during the interim analyses. The trial will be stopped if:

- The 3 month adverse event rate is determined to be in excess of 10%.
- A one-year local recurrence rate is more than 5%.

Assume the probability of 3 month adverse event (or 1 year local recurrence) is  $p$ , allowable maximum adverse event rate (or 1 year local recurrence rate) is  $p_0$  and the type I error is  $\alpha$ . The early stopping rules are based on the following statistical hypothesis test:

$$H_0: p \leq p_0 \quad \text{vs} \quad H_A: p > p_0$$

Based on the exact probability of Binomial distribution, we will reject the null hypothesis (i.e. stop the trial) if we observe  $k$  or more adverse events (local recurrences), where

$$k = \min \left\{ l : \sum_{i=l}^n \binom{n}{i} p_0^i (1 - p_0)^{n-i} \leq \alpha / 2 \right\},$$

and  $n$  is the number of patients at the time of the interim analysis.

The trial will be stopped if the 3 month adverse event rate is in excess of 10%. The trial will also be stopped if the 1-year local recurrence rate is more than 5%. The following table is based on  $\alpha = 0.05$ .

Minimum number of adverse events during first 3 months to stop the trial	Minimum number of local recurrences during the first 1 year to stop the trial	Number of patients treated
3	2	6
4	3	12
5	4	18
6	5	24

Safety analysis will be performed on all patients enrolled in the study. The incidence and its confidence interval of 3 month adverse events and 1 year local recurrences will be estimated. The time to local recurrence is calculated from the date of completion of radiation. Data for patients who remain free of local disease are censored as of date when the last follow-up information is obtained. At the end of the study, the cumulative local recurrence rate will be estimated by Kaplan-Meier method (46) for all patients (intend-to-treat) and 5-year recurrence rate will be then obtained and compared with those in the literature. The overall incidence and its confidence interval of acute complications following lumpectomy will be estimated. Also, we will estimate the overall incidence and the degree of fibrosis as defined on four-level scale of cosmetic outcome in appendix I.

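### Section 8's stopping sentences, formula and table disagree, the rule's limited power is not disclosed, and each recurrence look waits a year with enrolment open, so a boundary already crossed need not be acted on

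*Combined protocol and SAP*

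**What the plan says.** All of this is in Section 8.0 unless noted.

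- **Stopping sentences.** The trial stops if "The 3 month adverse event rate is determined to be in excess of 10" per cent, or if "A one-year local recurrence rate is more than 5" per cent. Both limits are repeated just above the table.
- **Test.** The rule is then framed as a test of H0: p ≤ p0 against p > p0: "we will reject the null hypothesis (i.e. stop the trial) if we observe" k or more events. Here k is the smallest count whose upper binomial tail at p0 is at most α/2. The table is said to use α = 0.05.
- **Table.** Minimum counts at n = 6, 12, 18, 24 are 3, 4, 5, 6 adverse events and 2, 3, 4, 5 recurrences. The n column is labelled as patients treated.
- **Timing.** "interim analyses will be performed after 6, 12, 18 and 24 patients have reached 3 months and 1 year post treatment period". Accrual is not paused while a look is under way: "The protocol will remain open to enrollment during the interim analyses".
- **Accrual.** "Thirty patients will be enrolled for this study and we expect to finish the enrollment within 5 years".
- **Other oversight.** Section 5.4 has a committee review serious adverse events, toxicity reports and annual reviews. It gives no numerical trigger.

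The plan gives no stopping probability at any true rate.

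**The concern.** Three statements of one rule should give one answer, and here they need not. With one adverse event or one recurrence in the first six patients (1/6 = 17%), the sentences can be read as an instruction to stop, while the table says continue. With 4 adverse events in 12, the table says stop and the formula says continue.

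A committee reading the 10% and 5% sentences may also believe that the trial is more tightly guarded than it is.

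The timing adds to this. A recurrence boundary can be reached among the first n patients months before the last of them completes one year. Nothing in the plan requires action in that interval, while further patients are enrolled and re-irradiated. The table and the text also differ on the denominator (treated, or having reached the time point). At the first recurrence look, under the accrual assumed below, these are 12 and 6.

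**Working it through.** **1. Reproducing the table.** Inputs from Section 8.0: p0 = 0.10 (adverse events) and 0.05 (recurrence), α = 0.05, tail level α/2 = 0.025. For each n, k is the smallest l with P(X ≥ l | n, p0) at or below the tail level.

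| n | AE printed | tail at printed k | AE at 0.025 | AE at 0.05 | LR printed | tail at printed k | LR at 0.025 | LR at 0.05 |
|---|---|---|---|---|---|---|---|---|
| 6 | 3 | 0.0159 | 3 | 3 | 2 | 0.0328 | 3 | 2 |
| 12 | 4 | 0.0256 | 5 | 4 | 3 | 0.0196 | 3 | 3 |
| 18 | 5 | 0.0282 | 6 | 5 | 4 | 0.0109 | 4 | 4 |
| 24 | 6 | 0.0277 | 7 | 6 | 5 | 0.0060 | 5 | 4 |

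(AE = adverse events, LR = local recurrences.)

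At 0.025, four of eight entries differ: AE at 12, 18 and 24, and LR at 6. At 0.05 the AE column is reproduced, but LR at 24 is 4, not 5. No single level gives the LR column: 2 of 6 needs a level of at least 0.0328, while 5 rather than 4 of 24 needs one below P(X ≥ 4 | 24, 0.05) = 0.0298.

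**2. Observed rates needed to stop (printed counts).** AE: 3/6, 4/12, 5/18, 6/24 = 50, 33, 28, 25%. LR: 2/6, 3/12, 4/18, 5/24 = 33, 25, 22, 21%.

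**3. Chance of stopping (printed counts).** Exact recursion: at each look, add six patients' binomial events to the running count, remove the paths at or above k, and sum what was removed. The first look can be checked directly: P(X ≥ 3 | 6, 0.20) = 0.0989 and P(X ≥ 2 | 6, 0.10) = 0.1143.

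| True rate | Look 1 | Look 2 | Look 3 | Look 4 |
|---|---|---|---|---|
| AE 10% | 1.6% | 3.3% | 4.6% | 5.6% |
| AE 20% | 9.9% | 22.7% | 33.3% | 41.7% |
| AE 30% | 25.6% | 52.9% | 70.4% | 81.1% |
| LR 5% | 3.3% | 4.2% | 4.5% | 4.7% |
| LR 10% | 11.4% | 16.3% | 19.0% | 20.6% |
| LR 15% | 22.4% | 33.1% | 39.6% | 44.2% |

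With the counts that the printed formula gives, stopping at twice the limit falls to 25.4% (AE) and 16.2% (LR).

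**4. Timing.** Assume even accrual, 60 months / 30 patients = one every 2 months, with treatment at enrolment. Patient n is treated at month 2n.

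- Recurrence look: month 2n + 12, with (2n + 12)/2 = n + 6 enrolled. Looks fall at months 24, 36, 48 and 60 with 12, 18, 24 and 30 enrolled. At most 18, 12, 6 and 0 patients can be spared.
- Adverse event look: month 2n + 3. At n = 24 this is month 51 with about 25.5 enrolled, so about 4 can still be spared.
- Range: if accrual takes 3 years, 16, 22, 28 and 30 are enrolled at the recurrence looks. At the last recurrence look, 29 are enrolled if accrual takes 6 years and 27 if it takes 10.

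**5. What earlier action would gain.** Simulation of 20,000 trials: printed recurrence counts, exponential time to recurrence, complete follow-up, 60-month accrual. Acting at the scheduled look is compared with acting when the k-th recurrence is detected among the first n treated. The detection patterns are assumptions. Section 7.0 has clinical visits every 3 months in year one, an ipsilateral mammogram at 6 months and then annual mammograms.

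| Detection | Mean treated in stopped trials, 20% recurrence | Spared per trial, all trials, 10% recurrence |
|---|---|---|
| Instant | about 17 to 12 | about 1.0 |
| At 3-monthly visits | about 17 to 13 | about 0.8 |
| At 6 and 12 months only | about 17 to 14 | about 0.6 |

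If every recurrence were found only at 12 months, the first comparison would be about 17 to 15. At 20% recurrence, 67% of trials stop under either timing.

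**The case against.** - **The percentages are p0, not the rule.** This largely stands. The first sentence asks that the rate be determined to exceed 10%, and the text then bases stopping on a hypothesis test. A reader might infer that the plan commits to stopping at any observed rate above 10% or 5% and then breaks that promise. Read as a whole, Section 8.0 does not support this, and a boundary above p0 is normal for a test that controls error. Nor would the literal rule be a better one: at exactly the allowed rates it would stop 67.5% (adverse events) and 61.6% (recurrence) of trials. The loose wording and the conflict between formula and table remain.
- **Low power is what 24 patients give.** This stands. Acting earlier changes when a stop happens, not whether it happens. The case is for disclosing the power.
- **Earlier action is not forbidden.** True: the plan schedules formal looks and has committee review under Section 5.4. But neither section requires action when a count is reached between looks.
- **The gain is modest at plausible rates.** This stands. The fall from about 17 to 12 needs recurrence at four times the limit and instant detection. At twice the limit, the average saving is one patient or fewer per trial.
- **The denominator is only a label.** Largely so, since the text defines who is counted. It still needs to match the rule.

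**Conclusion.** The point holds in two parts.

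First, the sentences, formula and table in Section 8.0 do not define one rule. Four of eight counts differ from the printed formula, and no single tail level gives the recurrence column. The operating characteristics are also missing. With the printed counts, 58% of trials at a 20% adverse event rate and 79% at 10% recurrence would pass all four looks. These figures are exact for the printed counts and would change with reconciled ones.

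Second, recurrence looks lag by a year with enrolment open, and a boundary already crossed triggers no stated action until the look. A reader might infer that the final look protects nobody at all. That is true only of the recurrence look at n = 24, and only if accrual is even and finishes on time or faster. The adverse event look at 24 could still spare about 4 patients, and slower or late-slowing accrual would leave a few for the recurrence look too.

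The savings rest on exponential recurrence times, treatment at enrolment, complete follow-up and the assumed detection patterns.

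**What to change.** In Section 8.0, in this order:

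1. Reconcile the formula, the alpha level and the table, so that every count follows from one stated tail level. Do this first, because the later steps would otherwise fix unreconciled counts in place.
2. Replace the sentences on exceeding 10% and 5% with: *the trial will be stopped if the count in the reconciled table is reached*. Keep 10% and 5% as p0.
3. Add: *each row applies as soon as the k-th qualifying event is confirmed among the first n treated patients, without waiting for the remainder to reach 3 months or 1 year.* The same patients and events are counted, so with complete follow-up the stopping probability is unchanged. The column label for patients treated then matches the rule.
4. Print the cumulative stopping probabilities at one, two and three times each limit, recomputed from the reconciled counts.

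The cost is a revision of Section 8.0 and a running event count kept by the study coordinator. No extra patients or visits are needed. The stated protection will look less favourable once the probabilities are printed. Step 3 improves timing only.

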One possible attraction for many women who select breast conservation as their treatment, is that if it “fails,” only then would they have to have a mastectomy—i.e. they have an initial opportunity to save their breast. The psychological impact of losing one’s breast is difficult for some women to accept. The term “salvage” mastectomy has been applied to the setting in which a patient who was initially treated with partial mastectomy and radiation therapy, and who develops an ipsilateral breast tumor recurrence (IBTR) then undergoes a mastectomy. The reasons behind the idea of a salvage mastectomy are several—first, since radiation treatments for breast cancer currently target the whole breast for the majority of the treatment period, by re-irradiating the breast, one would risk the possibility of unacceptable tissue damage, including necrosis and increased incidence of secondary malignancies. Just like all normal tissues, normal breast tissue has a limit as to how much radiation it may receive before the damage becomes irreparable. Second, the breasts of many patients who develop an IBTR may not be able to accommodate a second lumpectomy—i.e., cosmetic outcome can be affected, particularly with inferiorly located recurrences. Finally, studies have shown that patients who elect to have their IBTR removed with a lumpectomy (*without* repeat radiation) may have recurrence rates that can be as high as 35%, which is unacceptably high for most women (18). When counseling a woman considering a salvage mastectomy, it must be made clear that re-recurrence rates (i.e. a 2nd recurrence, this one after the mastectomy) have ranged from 2-32% of patients (19, 20).

Overall survival after mastectomy for an IBTR in a patient previously treated with breast conservation ranges from 52-84% at 5 years, (21, 22). As one might expect, invasive recurrences have a poorer prognosis than do noninvasive (23). Deaths after a noninvasive IBTR occur infrequently—deaths after an invasive recurrence occur more frequently and are often associated with metastatic disease. Having an IBTR increases the rate of developing distant metastases, as well as increases the risk of dying, when compared to women without an IBTR (24).

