A corollary can be made to an IBTR in a patient previously treated with breast conservation, that it may be possible, with modern diagnostic equipment, including breast MRI, to identify patients with known unifocal IBTR that may be able to be treated with focal radiation, thus avoiding a mastectomy. There is very little data in the literature looking at re-irradiation for patients with ipsilateral breast cancer recurrences. The largest of which is at report is from The University of Pittsburgh. Deutsch et al, treated 39 patients with repeat radiation therapy for breast cancer—31 invasive and 8 *in situ* cancers. Patients were treated with en-face electrons to a total dose of 5000cGy, directed only at the cavity of the IBTR excision (i.e. partial breast with linac). At last follow-up (median 51.5 months, range 1-180 months), 76.9% of patients had an intact breast free of tumor. At 5 years, overall survival was 78% and disease free survival was 69%. Importantly, no late sequelae of repeat radiation therapy developed other than skin pigmentation changes—cosmetic outcome was reported as good to excellent in 69% of patients (26). There were no rib fractures, pulmonary problems or secondary malignances, despite areas of the breast being exposed to more than 10,000 cGy. All patients except one finished the radiation treatments (RT was discontinued for nonmedical reasons). Distant metastases developed in 8 women (2 with concerning bone scans at the time of diagnosis of IBTR), and 7 of these women died 21-71 months after re-irradiation. Two of the women who developed distant metastases first developed a contralateral breast cancer. Eight women developed a 2nd IBTR after re-irradiation (2 of which had positive axillary lymph nodes), and only 3 of which were in the same quadrant as the first.

A group in France utilized post-operative brachytherapy in a small series of patients who opted for repeat breast conservation after IBTR—some refused mastectomy, and some were not candidates—they were treated to a dose of 30 Gy (dose rate not mentioned) (27). Four (26%) of patients developed a 2nd IBTR at a median follow-up of 4 years. There are several criticisms of this study, including the lack of reporting of margin status, or brachytherapy dose rate. Three patients had “major” cosmetic sequelae (one with locally treated skin necrosis), but cosmetic analyses/comment is only available for 8/15 patients involved in the study.

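### No prespecified stopping rule counts toxicity after month 3; later tissue damage reaches only a committee review with no stated threshold

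*Combined protocol and SAP*

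**What the plan says.** Section 8.0 schedules two sets of looks for patient safety: "interim analyses will be performed after 6, 12, 18 and 24 patients have reached 3 months and 1 year post treatment period". Enrolment stays open while they are done.

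Two triggers are attached:

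- Toxicity: "The 3 month adverse event rate is determined to be in excess of 10" per cent.
- Recurrence: "A one-year local recurrence rate is more than 5" per cent.

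The column headings of the stopping table keep the same windows: "Minimum number of adverse events during first 3 months to stop the trial" (3, 4, 5, 6 events at 6, 12, 18, 24 patients) and "Minimum number of local recurrences during the first 1 year to stop the trial" (2, 3, 4, 5 recurrences). Section 8.0 does not say which adverse events qualify.

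Outside Section 8.0, Section 5.4 states: "The Data and Safety Toxicity Committee will review all serious adverse events and toxicity reports as well as annual reviews". It gives no 3-month limit, no threshold and no explicit power to halt enrolment, and it refers to an institutional monitoring plan that is not among the documents.

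On the harm itself, Section 1.0 says that by re-irradiating the breast "one would risk the possibility of unacceptable tissue damage, including necrosis and increased incidence of secondary malignancies".

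**The concern.** The 1-year looks exist, but the only event counted at them is local recurrence, which is an efficacy outcome. A necrosis or ulceration first seen in month 4 belongs to neither column of the table at any look. Yet tissue damage is the first reason Section 1.0 gives for salvage mastectomy, so the written rule may close before the harm it should guard against has appeared.

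The final analysis does not close the gap. Its timed safety estimates in Section 8.0 are again 3-month adverse events and 1-year recurrences. Fibrosis is to be estimated but is tied to no stopping rule.

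Enrolment may run for up to 5 years, so early patients could have a year or more of follow-up while others are still being treated. Whether an excess of late damage halts enrolment would then rest on discretion alone.

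**Working it through.** **Inputs from Section 8.0.** Looks at n = 6, 12, 18, 24; toxicity limit p0 = 10%; α = 0.05; 30 patients within 5 years.

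**Assumptions.** The documents do not give the timing or rate of re-irradiation damage. I assume a total 1-year complication rate of 30% (20% as a second case), a share f of it first appearing after month 3, independence between patients, and even accrual of 30/60 = 0.5 patients per month.

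**Step 1: the plan's counts.** The formula takes the smallest k with P(X ≥ k | n, p0) ≤ α/2 = 0.025. At p0 = 10% it gives 3/5/6/7, not the printed 3/4/5/6; for example, P(X ≥ 4 | 12, 0.10) = 0.0256, just above 0.025. A one-sided cut of 0.05 gives 3/4/5/6. That mismatch is a separate matter, so results are shown for both sets.

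**Step 2: chance of crossing.** Six new patients are added at each look. The exact binomial distribution of the cumulative count is carried forward among trials not yet stopped, and the probability of reaching k is summed over looks.

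| True rate counted | Printed, 3 looks | Printed, 4 looks | Formula, 3 looks | Formula, 4 looks |
|---|---|---|---|---|
| 10% | 4.6% | 5.6% | 2.1% | 2.4% |
| 20% | 33% | 42% | 19% | 25% |
| 30% | 70% | 81% | 53% | 67% |

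**Step 3: which looks can still spare patients.** The 1-year look for n patients falls at month n/0.5 + 12, that is months 24, 36, 48 and 60. By then 12, 18, 24 and 30 are enrolled, leaving 18, 12, 6 and 0. Only the first three 1-year looks can prevent an enrolment. The 3-month looks fall at n/0.5 + 3, that is months 15, 27, 39 and 51, all during enrolment, so all four count.

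**Step 4: the 3-month rule when part of the toxicity is late.** The rate it can see is 30% × (1 − f). Its four-look stopping chance is:

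| f | Rate seen by month 3 | Printed counts | Formula counts |
|---|---|---|---|
| 25% | 22.5% | 53% | 35% |
| 50% | 15% | 20% | 10% |
| 75% | 7.5% | 2% | 1% |
| 100% | 0% | 0% | 0% |

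Against these, counting the same events to 1 year with the same counts stops 70% (printed) or 53% (formula) by the third 1-year look.

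**Step 5: the lower rate.** At 20% by 1 year, the three-look figures are 33% and 19%. The 3-month rule with f = 50% sees 20% × 0.5 = 10% and stops 5.6% or 2.4%.

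**Step 6: faster accrual.** Section 8.0 says within 5 years, so 5 years is the slow end. Even accrual over 3 years leaves 14, 8 and 2 patients at the first three 1-year looks; over 2 years, 9, 3 and 0. In the 2-year case only two looks are useful, and at a 30% rate they stop 53% (printed) or 36% (formula). That is about level with the 3-month rule at f = 25% and still well above it at f = 50% or 75%.

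**The case against.** The strongest objection is Section 5.4. A reader might infer from Section 8.0 that late toxicity can never stop the trial, or that the plan tells the committee to continue however many patients are harmed. The documents do not support that. Section 8.0 says when the trial will be stopped and nowhere orders continuation otherwise. A necrosis in month 4 falls within the committee's review of serious adverse events, and the institutional plan that Section 5.4 adopts may give it authority to suspend enrolment. This stands, and it limits the point to the absence of a prespecified, quantified rule.

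The evidence in Section 1.0 is also mixed. The French series reports three patients with major "cosmetic sequelae (one with locally treated skin necrosis"), but it has 15 patients, cosmetic comment on only 8 of them, and no timing for the necrosis. The largest series (39 patients, median follow-up 51.5 months) saw no late sequelae beyond pigmentation changes, no rib fractures and no pulmonary problems. The Austrian series reports no unacceptable cosmetic results. So the documents do not show that late damage is frequent. They show that the protocol regards it as a principal risk.

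Finally, the 30% rate and the late shares are assumed, and at 20% a 1-year count would miss most trials by the third look. That is fair. What needs no assumption is that events after month 3 add nothing to the chance of a rule-based stop.

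**Conclusion.** The point holds in this form: no prespecified stopping rule counts toxicity after month 3, and later toxicity reaches only an unquantified committee review whose stopping authority the documents do not state. How much this matters depends on how much toxicity is late. With a 30% one-year rate and half of it late, rule-based stopping is 20% (printed counts) or 10% (formula counts), against 70% or 53% by the third 1-year look if the same events were counted to 1 year. The gap is smaller if most damage is early or accrual is fast.

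A reader might credit the 1-year count with the four-look figures of 81% and 67%. Under even 5-year accrual the fourth look falls at about month 60, with all 30 patients enrolled, so those figures overstate the useful gain. This is a gap in the monitoring plan that should be closed; it does not invalidate the trial's estimates.

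**What to change.** Reconcile Section 8.0 with Sections 1.0, 5.4 and 6.4. At the 1-year looks already scheduled, add cumulative treatment-related toxicity from treatment to 1 year to the counts reviewed. Test it with the plan's exact binomial method and report it to the existing Data and Safety Toxicity Committee, and state what the committee may do on a crossing. Which events qualify and what limit applies are clinical choices. The sponsor's clinicians should set both before the first look; this review proposes neither.

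The cost is one paragraph and one column in the stopping table. No new visits are needed: Section 7.0 already has clinical evaluation every 3 months in the first year, and complications are endpoint 6.4. Sections 7.0 and 9.0 differ on cosmetic follow-up only after year 1, which does not affect a 1-year count.

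The statistical downside is a small added chance of a false stop. If, for example, the limit were the plan's existing 10% and the true 1-year rate equalled it, that chance would be about 2.4% (formula counts) to 5.6% (printed counts) over four looks.
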